3.7 Recruitment, allocation concealment and blinding

The 70 classes will be selected through stratified randomisation, with stratification for schools and grades (9th, 10th, 11th and 12th) from the overall sampling frame of 118 classes (54 classes had received classroom sensitisation in earlier pilot work). The stratification is proposed to ensure a similar composition of classes across schools in both the sequences. The detailed step by step description of the stratified randomisation is placed at the appendix.

No allocation concealment or blinding is planned as the intervention providers as well as the researchers recording referrals will be aware of the allocation of the classes.

3.8 Data collection and management

3.8.1 Data collection

Data will be sourced from the following sources:

- 1. Referral logs maintained by school-based researchers recording the numbers and sources of referrals to the PRIDE counselling service. Case by case information on the referrals received is collected via the tablets digitally including the self-reported student data such as class, gender and age obtained at the time of referral and assessment.
- 2. Logs for the school-level and the classroom level sensitization that are recorded on the sensitization logs.
- 3. Strengths and Difficulties Questionnaire completed by students on digital tablets as part of the standard eligibility screen for the PRIDE counselling service/host trial.
- 4. Additionally, the classroom information and engagement sessions, and the data collection process will be audio-recorded or assessing fidelity of the intervention.

3.8.2 Data management

Data will be collected digitally using the customized STAR software program(11), and will be remotely uploaded as comma-separated values (CSV) files on a secured server. The date and time stamps for original data entry will be included, and an audit trail documenting any subsequent changes will be maintained. All paper-based data will be entered manually in SQL Epi-info forms and linked by participant ID with digitally collected data. Range and consistency checks will be performed at weekly intervals, with all inconsistencies and corrections logged to maintain an audit trail. All data will be anonymized and backed-up on external hard disks on a daily basis.

All referred adolescents will receive a unique identification number (student ID) which will be included on the SDQ forms and other process data documents. These IDs will include codes for school, grade, division and a unique serial number. The names and contact details received from students as a part of referral process will be stored separately. The name and the student ID will never be used together in any document, to ensure confidentiality.

Access to pre-locked data will be password-protected at multiple levels. After the dataset is locked, it will remain password-protected and trial investigators will have access to the datasets.

4. Variables

4.1 School, class and Demographic variables

The following school, class and demographic data will be included in the data-set for all the referred adolescents. From students who refuse participation in the study, reasons for such refusal will be additionally collected.

- Student ID
- School ID
- Class ID
- Age
- Gender
- Reason for exclusion from the trial
- Reason for refusal to participate in this trial

Additionally, following class level data will be recorded:

- Class ID
- School ID
- Allocation to sequence
- Time period for receiving classroom sensitization
- Number of students in the class
- Number of boys in the class
- Number of girls in the class

4.2 Outcome variables

The following outcome variables will be prepared at the student level. All individual data pertaining to the variables of referral, referral source, and assessment using SDQ, will be collected only from referred students. Data will be organised in the long format and record the following variables. A codebook will be developed explaining all the variables included in the data sheet.

- Time period of receiving classroom sensitization
- Referral status in each of the three time periods of the trial
- Date of referral
- Eligibility to receive counselling for all referred students (binary variable), determined through the following (table 1):
 - Total Difficulties score on SDQ
 - o Impact score
 - Chronicity
- Scores for symptom sub-types:
 - Externalising score = the sum of the conduct and hyperactivity scales
 - Internalising score = the sum of the emotional and peer problems scales
- Source of referral: categorized as self-referral and others

4.3 Intervention delivery and fidelity variables

1. Control condition:

School based sensitization activities are reported by the school counsellors using the Intervention logs. These include the following:

1) Display of posters and drop-box

- Number of posters displayed in the school
- Number of drop-box installed in the school

2) Meetings with school principals and teachers:

- Number of teachers attending the meeting in the school
- Duration of the teachers' meeting (minutes)
- Number of meetings held with school Principals
- Duration of the meetings with Principals (minutes)

2. Intervention condition:

Classroom sensitization sessions are also recorded in the intervention logs maintained by school counsellors. These include the following:

- Date of Classroom sensitization received in the time period
- Number of students attending the sensitization session
- Duration of the sensitization session (minutes)
- Fidelity rating provided by an independent provider for 20% of all the sessions conducted.

4.4 Severe adverse events

There are no severe adverse events (SAE) anticipated from the participation in the classroom sensitization sessions and referral and assessment of students. Any potential harms or SAE discovered during the assessment will be recorded and reported along the protocol developed for the PRIDE trials(1).

5. Data analysis plan

Quantitative analysis will be conducted using STATA (version 15.1). Findings will be reported as per CONSORT extension for reporting of stepped-wedge cluster randomised trials for the embedded recruitment trial(12).

5.1 Baseline characteristics of the participants by randomised sequence

The baseline characteristics of the participating 70 classes, including grade, gender composition, will be described across each of the two sequences of allocation. As the allocation of classes is based on stratified randomisation, no systematic differences are expected across the two conditions.

			. .						
Tahle 2	Raceline	characteristics	of the	rlaccoc	randomiced	in pa	ch of th	e two	seallences
rubic z	Duschine	characteristics	oj une	ciusses	runuonniscu	in cu	ch oj th		Sequences

	Total	Sequence 1		Sequence 2	
	N (%)	N	%	N	%
Gender:					
Male					
Female					
Grade:					
9 th					
10 th					
11 th					
12 th					
School:					
GBSSS, Mahipalpur					
GBSSS, Molarband					
SBV, Molarband					
GGSSS, Molarband					
ASMS-SKV, Mahipalpur					
SBV Co-Ed, Vasant Vihar					

5.2 Recruitment and representativeness of participants

The number of adolescents not available or refusing to participate in the trial will be reported, overall and within each condition. The reasons for exclusion and refusal to participate will be summarized. Additionally, adolescents lost to follow-up post referral will also be reported, overall and within each condition.

Differences between adolescents consenting to participate in the trial and those refusing to participate or lost to follow-up will be assessed for differences in age, gender, grades and school, severity of mental health symptoms and eligibility to receive problem solving intervention, if their SDQ score are available.

Characteristic (all	Total		Consenting to		Refusing to		Statistic
Classes)			participate in trial		participate or lost		
					to follow-up		
	Ν	%	n	%	n	%	
Age (Mean (SD))							T-test
Gender							McNemer's
Female							Chi square
Male							

Table 3 Characteristics of the participants in the trial

Characteristic (all	Total		Consenting to		Refusing to		Statistic
Classes)			participate in trial		participate or lost		
					to follow-	-up	
	Ν	%	n	%	n	%	
Grade							McNemer's
9 th							Chi square
10 th							
11 th							
12 th							
School							McNemer's
GBSSS, Mahipalpur							Chi square
GBSSS, Molarband							
SBV, Molarband							
GGSSS, Molarband							
ASMS-SKV, Mahipalpur							
SBV Co-Ed, Vasant Vihar							
Total SDQ score							T test
(Mean, SD)							
Proportion of students							McNemer's
eligible for receiving							Chi square
problem solving							
intervention							

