3.1 Trial Design

The trial will be implemented as a Stepped Wedge Cluster Randomised Controlled Trial (SW-CRCT). The essential feature of a SW-CRCT is that random allocation determines the time period in which clusters begin an intervention. All clusters start with the first time period of control intervention, and cross-over from the control to the intervention condition across pre-defined time periods, in a random, but sequential, order(4).

We will select 70 classes using stratified randomisation to represent each of the grades 9th, 10th, 11th, 12th across the six participating schools in Delhi with probability proportional to size.

		Step 1	Step 2	Sequence of receiving treatments*
Sequence 1 (1-35 classes)	Control condition	Intervention condition	Intervention condition	011
Sequence 2 (36-70 classes)	Control condition	Control condition	Intervention condition	001
Time	1 st time period (4 weeks)	2 nd time period (4 weeks)	3 rd time period (4 weeks)	

Figure 1: Illustration showing implementation of the control and intervention conditions.

Notes: The white boxes indicate the group of classes in the control condition and the coloured boxes indicate the group of classes in the intervention condition. *0=control condition; 1=intervention condition The 70 classes will be randomised to be a part of either of 2 sequences as shown in Figure 1. A small block size of 2 will be used to allocate the 70 classes across the two sequences in order to ensure balance, as the number of classes within each grade from the individual schools is relatively small. In the rare instance that a selected class has been dissolved or merged with another class, the next class in the random list will be included to replace the unavailable class. Each sequence will be implemented over three consecutive 4-week intervals. The trial will be conducted over 12 weeks except for breaks due to exams and holidays. All classes will begin with the control intervention period of 4 weeks, where only school level activities will be rolled out.

Notes: The white boxes indicate the group of classes in the control condition and the coloured boxes indicate the group of classes in the intervention condition.

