3.2 Study setting

The trial will be conducted in six Government-run secondary schools in New Delhi, India. The schools were purposively selected in consultation with the Department of Education, Government of New Delhi, to focus on relatively under-served, low-income communities. Of the six schools, three are boys' schools, two are girls' schools and one is co-educational. As of August 2018, there were 172 classes in grades $9^{th} - 12^{th}$ with a total student population of 8448 (ranging from 1050 to 1632 per school; mean=1408, SD=225), including 4694 (56%) boys and 3754 (44%) girls.

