6.5 Statistical considerations

95% confidence intervals and p-values will be calculated for all outcomes.

Intention to treat analysis: All the classes randomised to receive the classroom sensitization intervention throughout the trial will be included in the analysis and will be considered to be in the respective condition to which they were assigned initially, irrespective of the receipt of the intervention.

Missing data: The number (%) of participants with complete data will be reported. The primary analyses will be complete cases, with adjustments made for baseline variables which are associated with the outcome and/or missingness, to account for missing data.

No interim analysis of outcomes will be undertaken.

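### Table 3 names McNemar's chi-square, a paired-data test, to compare two separate groups of students; it misleads for gender and eligibility and cannot be formed for grade or school

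*SAP*

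**What the plan says.** Section 5.2 of the SAP plans a check on how far participants resemble non-participants: "Differences between adolescents consenting to participate in the trial and those refusing to participate or lost to follow-up will be assessed". The characteristics to be compared are "age, gender, grades and school, severity of mental health symptoms and eligibility to receive problem solving intervention, if their SDQ score are available".

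Table 3 sets this out with one column for consenting students and another for students who refused or were lost. Its Statistic column gives a t-test for age and total SDQ score. For gender, grade, school and eligibility it gives McNemar's chi-square (with the name misspelt). No other section names a different test for this table, and nothing in the SAP describes matching or pairing of the two groups.

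Section 6.5 adds that the primary analyses are complete-case, "with adjustments made for baseline variables which are associated with the outcome and/or missingness". It does not say how those variables will be identified.

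**The concern.** McNemar's test is for paired binary data: the same person measured twice, or matched pairs. It uses only the two discordant cells of a square table whose rows and columns record the same binary variable. In Table 3 a student is either consenting or not, and the rows record another characteristic altogether. The discordant cells therefore have no meaning here.

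Two consequences follow.

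- **Gender and eligibility (2 by 2).** Software will return a p-value, but it does not test whether the groups differ in composition.
- **Grade and school.** The trial covers "grades 9th, 10th, 11th, 12th across the six participating schools in Delhi", so these tables are 4 by 2 and 6 by 2. Neither McNemar's test nor its extensions to larger square tables can be formed, so the plan leaves these rows without a usable test.

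At stake is the SAP's only formal comparison of participants with non-participants. If the same p-values were used to pick the adjustment variables in section 6.5, the error would spread further, but the SAP does not say that they will be.

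**Working it through.** The SAP states no figure for Table 3, so there is nothing to reproduce. The check shows what the named test does on tables of this shape.

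**Inputs**

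- Share of girls: 44%, from section 3.2 ("including 4694 (56%) boys and 3754 (44%) girls"). This is the whole-school share, used only for illustration.
- Number of referred students and the split between consenting and refusing or lost: not in the SAP. Assumed: 250 students, with several splits.

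**Formulas.** Take the gender row in Table 3's order (Female, then Male), with columns consenting and refusing or lost:

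| | Consenting | Refusing or lost |
|---|---|---|
| Female | a | b |
| Male | c | d |

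- McNemar: (b − c)² / (b + c), 1 df, no continuity correction.
- Pearson: N(ad − bc)² / (product of the four margins), 1 df, uncorrected.

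Since girls = a + b and consenters = a + c, b − c equals the number of girls minus the number of consenters. The test therefore asks whether there are as many girls as consenters, which has no bearing on representativeness.

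**Identical composition (44% girls in both groups; Pearson = 0, p = 1 in every row)**

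| Consenting v not | b (refusing girls) | c (consenting boys) | McNemar | p |
|---|---|---|---|---|
| 225 v 25 | 11 | 126 | 115²/137 = 96.53 | about 9e-23 |
| 200 v 50 | 22 | 112 | 90²/134 = 60.45 | about 8e-15 |
| 150 v 100 | 44 | 84 | 40²/128 = 12.50 | 0.0004 |
| 125 v 125 | 55 | 70 | 15²/125 = 1.80 | 0.18 |

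The statistic follows the group sizes. Composition is the same throughout.

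**Row order.** Take 150 v 100 again with Male listed first: b = 56 refusing boys, c = 66 consenting girls, and McNemar = 10²/122 = 0.82 (p = 0.37). The same data gave p = 0.0004 with Female first.

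**A real difference missed.** Let consenters be 100 girls and 50 boys (67% girls) and non-participants 50 girls and 50 boys (50% girls).

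- McNemar, Female first: b = 50, c = 50, statistic 0 (p = 1).
- Pearson: 250 × (100×50 − 50×50)² / (150×100×150×100) = 6.94 (p = 0.008).
- McNemar, Male first: b = 50, c = 100, statistic 50²/150 = 16.67 (p about 0.00004).

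**Simulation under no association** (20,000 tables per scenario, 56% boys, boys listed first, students independent; consent share and N assumed):

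| Consent share | McNemar rejects, N = 200 | McNemar rejects, N = 500 |
|---|---|---|
| 50% | 23% | 48% |
| 80% | 99.9% | 100% |
| 90% | 100% | 100% |

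Pearson rejects in 5.1% to 5.3% of tables in every scenario, against a nominal 5%.

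**Grade and school.** McNemar's test needs equal numbers of rows and columns. Table 3 has four grades by two groups and six schools by two groups, so the test is not defined for either.

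**The case against.** The strongest reply is that this is probably a slip of naming. The cell also contains the words chi-square, and the same label sits on a four-level and a six-level variable, where McNemar's cannot be run. An analyst would notice at once and use an ordinary chi-square. That may well happen for grade and school, and it softens the worry about choosing a test once the data are in. It does not help gender and eligibility, where the named test will run and return a number.

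Second, Table 3 is descriptive. The primary outcome is built from class sizes and referral logs, and no outcome model uses Table 3's p-values. The table also gives counts and percentages, which carry most of the message. This stands, and it limits the importance of the point. The link to section 6.5 is only a possibility.

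Third, the illustrative p-values rest on assumed group sizes. This is also true: they show how the test behaves and do not predict this trial's results.

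Fourth, Pearson's test assumes independent students, while these are nested in classes, and five of the six schools are single-sex. This has some force. As an illustration, assume 250 referrals over 70 classes (250/70 ≈ 3.6 per class) and a consent ICC equal to the referral ICC of 0.124 in section 3.6. The design effect is then 1 + 2.6 × 0.124 ≈ 1.3, and a nominal 5% test of a factor constant within class has a true level near 9%. Pearson's is far better than McNemar's here but not perfect, and the simulation above, which had no clustering, does not show otherwise.

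**Conclusion.** The point holds. Table 3 prespecifies a paired-data test for two mutually exclusive groups. For gender and eligibility the resulting p-value is uninformative: it can be extreme when composition is identical, can be 1 when composition differs, and depends on which row is listed first. For grade and school the test does not exist.

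That conclusion rests on the layout of Table 3 and the definition of the test, and does not depend on the assumed numbers. Its consequence is limited to the representativeness comparison. The primary, secondary and exploratory effect estimates are untouched unless Table 3 is used to select adjustment variables, which the SAP does not state. It should be corrected, but it does not threaten the trial's main result.

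**What to change.** In the Statistic column of Table 3, replace McNemar's chi-square with Pearson's chi-square in the gender, grade, school and eligibility rows, and state that Fisher's exact test is used where expected counts are small.

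A better option, given the nesting in classes, is to regress participation status (consenting or not) on each characteristic in turn, with grade and school as categorical predictors and standard errors clustered on class.

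The cost is the wording of four table cells, or one added sentence for the regression option. Data collection, sample size and the primary analysis do not change.

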3.6 Power calculation

We based our power calculation on a within-period comparison for a stepped wedge design(10), using Stata package "clustersampsi". Based on pilot data, we anticipated referral rates of 5% and 15% on the control and intervention conditions respectively, with an intra-cluster correlation coefficient (ICC) of 0.124. We assumed the same ICC for the between-time correlation given the short time period of follow-up. In practice, it may be smaller than 0.124 and both ICCs will be reported. Using these parameters, a sample size of 70 classes (average class size of 50 students) will have 92% power to detect a difference of 10 percentage points (treating the outcome as a binomial variable), at a significance level of 0.05.

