We have data with three records for each student, for time period 1, 2 and 3, with students nested in classes. The calculation of the parameters will need to account for this clustering of data at the class level. Analysis will be undertaken using Generalized Estimating Equations (GEE) with robust standard errors that are measured using the sandwich estimator method. GEE is a general statistical approach to fit a marginal model for longitudinal/ clustered data analysis. GEE was introduced by K. Liang and S. Zeger(13) to analyse longitudinal data without resorting to fully specified random effect models and can be applied to both continuous and categorical outcomes. It is a recommended method for analysis of the stepped wedge cluster randomised controlled trials(14), and provides population averaged effects of exposure to the interventions across the control and intervention conditions. GEE provides both parameter estimates and standard errors that are corrected for clustering of data and are consistent despite misspecifications in the correlation structure. For these reasons, GEE is a suitable method for analysis of primary outcome in this trial.

The analysis will be carried out using "xtgee" command using Stata 15.1. The panel structure of data and clustering of data at class level will be specified through stata command "xtset". The following will be specified in the GEE model:

- Family of distribution of the response variable: Binomial as the outcome variable is binary.
- Link function: Logit link function.
- The within-group correlation structure will be specified as independent.
- Standard error type: robust.

Having a variable for indicating the class in which student observations are nested (class_id), outcome variable indicating the referral status of the adolescent (referred), time indicator (t2) for period 2 for classes that continue to experience school based sensitization activities, indicators for the immediate and continued effects of classroom sensitization activities (effect_lag0 and effect_lag1), the parameters will be estimated using the stata command as illustrated below:

"xtset class_id"

"xtgee referred t2 effect_lag0 effect_lag1, family(binomial) link(logit) corr(independent) vce(robust)"

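### Table 3 tests refusal and loss without allowing for class, by t-tests and an inapplicable paired test; if refusal or loss clusters by class, the age, gender, grade and school rows reject too often

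*SAP*

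**What the plan says.** Section 5.2 plans a comparison of consenting adolescents with a second group, saying that "those refusing to participate or lost to follow-up will be assessed for differences in age, gender, grades and school", and also in symptom severity and eligibility where SDQ scores exist. The Statistic column of Table 3 assigns a t-test to age and to total SDQ score. It assigns McNemar's chi-square (spelt McNemer's) to gender, grade, school and the proportion eligible. Neither the text nor the table mentions class.

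The outcome models are handled differently. Section 6.2 says of its model: "The calculation of the parameters will need to account for this clustering of data at the class level". It uses GEE with robust standard errors grouped by class, and sections 6.3 and 6.4 follow it. The only class-level correlation in the SAP is in section 3.6, which anticipates referral rates "with an intra-cluster correlation coefficient (ICC) of 0.124". That value is for referral, not for refusal or loss after referral.

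Section 6.5 adds that the complete-case analysis will adjust for baseline variables related to the outcome or to missingness.

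**The concern.** There are two faults in one column.

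- **Paired test on unpaired groups.** The adolescents who consent and those who refuse or are lost are different people, so there are no pairs for McNemar's test to use. Grade has four levels and school six, so those rows are not binary either.
- **No allowance for class.** The t-tests treat classmates as independent, and so would the obvious replacement for McNemar's test. Grade and school are constant within a class, and age largely follows grade. Section 3.2 lists five single-sex schools out of six. By Table 1.2b the co-educational school supplies 10 of the 70 classes, so gender is constant in the other 60. For such characteristics, any class-to-class variation in refusal or loss can pass for an association.

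At stake is how the table is read: an apparent selective refusal by age, grade or school might be class-level variation only. If the covariates of section 6.5 are chosen from these p-values, the error could carry into that choice.

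**Working it through.** The SAP states no error rate for Table 3, so there is no figure to reproduce.

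**Inputs from the SAP.** 70 classes of about 50 students; the school-by-grade layout of Table 1.2b; referral rates of 5% (control) and 15% (intervention); a significance level of 0.05, given for the power calculation only and taken here as two-sided.

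**Assumptions.**
- 20% of referred students refuse or are lost.
- Refusal or loss is unrelated to any characteristic but may vary by class, with ICC 0 to 0.124.
- 15 or 5 referred students per class. If the rates apply to each 4-week period, sequence 1 yields 5 + 15 + 15 = 35% and sequence 2 yields 5 + 5 + 15 = 25%; the mean is 30%, and 30% of 50 = 15. The lower value, 5, is 10% of 50.
- Mean age rises one year per grade, with a within-grade SD of 1 year. The SDQ score has class ICC 0.124.

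**Approximation.** With m referred per class, DE = 1 + (m − 1) × ICC(characteristic) × ICC(refusal). The true two-sided error of a one-degree-of-freedom test is 2 × [1 − Φ(1.96/√DE)]. For a characteristic constant within class (ICC 1):

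- m = 5, refusal ICC 0.05: DE = 1 + 4 × 0.05 = 1.20; error 7.4%
- m = 15, refusal ICC 0.05: DE = 1 + 14 × 0.05 = 1.70; error 13.3%
- m = 5, refusal ICC 0.124: DE = 1 + 4 × 0.124 = 1.50; error 10.9%
- m = 15, refusal ICC 0.124: DE = 1 + 14 × 0.124 = 2.74; error 23.6%
- refusal ICC 0: DE = 1; error 5.0%

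Rows with more levels fare worse. The chi-square critical value is 7.815 for grade (3 df) and 11.070 for school (5 df). Dividing by 2.736 gives 2.86 and 4.05, which are exceeded with probability 41% and 54%.

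**Simulation.** 1,500 runs per setting on the Table 1.2b layout, with beta-binomial refusal by class; Monte Carlo standard error at 5% is √(0.05 × 0.95/1500) = 0.6 points. An unadjusted Pearson chi-square stands in for McNemar's test in the columns marked *. The eligibility row was not simulated. False-positive rates (%):

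| Referred per class | Refusal ICC | Age | Gender* | Grade* | School* | SDQ |
|---|---|---|---|---|---|---|
| 5 | 0 | 4.9 | 5.2 | 3.8 | 4.6 | 5.1 |
| 5 | 0.02 | 7.0 | 7.0 | 6.7 | 7.7 | 5.0 |
| 5 | 0.05 | 7.1 | 7.4 | 9.3 | 12.0 | 4.7 |
| 5 | 0.124 | 8.1 | 11.1 | 17.3 | 23.3 | 6.2 |
| 15 | 0 | 4.5 | 4.6 | 6.1 | 4.6 | 5.1 |
| 15 | 0.02 | 4.9 | 7.8 | 10.1 | 12.4 | 5.9 |
| 15 | 0.05 | 10.3 | 12.7 | 22.0 | 28.1 | 5.5 |
| 15 | 0.124 | 18.1 | 21.8 | 41.7 | 56.3 | 7.1 |

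**Check of the remedy.** In the same layout (1,000 runs per setting; refusal ICC 0, 0.05 and 0.124; 5 and 15 per class), a class-robust logistic Wald test with a chi-square reference gave about 5–6% for age, 7–10% for grade and 11–14% for school. The sandwich estimator is sound for age, somewhat liberal for grade, and not good enough for the six-level school row.

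**The case against.** The strongest reply is that this is a descriptive table. It also shows counts, percentages, means and SDs; section 5.2 sets no significance threshold or decision rule for it; and the primary estimate does not use it. A reader might infer that Table 3 decides whether the sample is called representative. The SAP does not say so. Nor does section 6.5 tie covariate choice to these p-values, so that consequence is possible only. These points stand and limit the importance of the finding.

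A reader might also infer that false positives will certainly be far too frequent. That needs refusal or loss to cluster by class, which the SAP neither states nor quantifies. Clustering is plausible, because sessions are given class by class with a researcher who also handles referrals and eligibility assessments. But students may also use a drop-box individually, and each SDQ assessment is timed from that student's own referral. Fifteen referred per class further requires the 15% rate to persist into sequence 1's second intervention period, after a one-off session. Hence the range, including no inflation at ICC 0.

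Third, the large grade and school figures belong to a substituted Pearson test. An error rate cannot be assigned to McNemar's test on groups where it cannot be computed. This stands; the definite fault in those rows is the paired test, and the clustering figures show what the natural repair would leave behind.

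Finally, the clustering sentence in section 6.2 concerns that section's model, so the SAP does not contradict itself. And since the six schools were purposively selected, a real imbalance between them matters whatever its p-value, which favours description for that row.

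**Conclusion.** The point holds in conditional form. As written, four rows of Table 3 name a test that does not apply, and no row allows for class. For age, the test the SAP names has a false-positive rate of about 7–18% under the stated assumptions (20% refusing or lost, 5 to 15 referred per class, refusal ICC 0.05 to 0.124). With an unpaired chi-square substituted, the range is about 9–42% for grade and 12–56% for school. With no clustering of refusal all are about 5%, and the SDQ row stays near 5–7% throughout. The upper ends borrow 0.124, the referral ICC, as a refusal ICC.

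The effect falls on the representativeness table and possibly on the choice of missing-data covariates. It does not reach the primary estimate directly. It is worth correcting before analysis because the table cannot be produced as specified and the correction is cheap.

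**What to change.** Replace the Statistic column of Table 3 with a logistic GEE of refused or lost (1) versus consenting (0) on each characteristic, grouped by class with robust standard errors as in section 6.2. This removes the paired test and allows for clustering together. Report school as proportions or standardised differences without a p-value. For grade, treat the robust p-value with caution or use a small-sample reference distribution, given the 7–10% found above.

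Alternatively, report the whole table descriptively without p-values, which is equally acceptable and simpler. Adding condition to the model is optional and not part of this correction.

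The cost is one table column and a few lines of Stata code, with no new data.
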